2.2.3.1. Study 217058 - Oral FTIH VH4004280

Study 217058 is an ongoing double-blind (sponsor unblinded), randomized, placebo-controlled, single and multiple-ascending-dose Phase 1 and FTIH study to evaluate the safety, tolerability and pharmacokinetics of VH4004280, when **CCI** in healthy adult participants. The study is also designed to evaluate the DDI potential of VH4004280 and evaluate the safety, tolerability and PK of a VH4004280 **CCI** in comparison with existing data from VH4004280 **CCI**

Based on preliminary results, 41 participants and 18 participants have been enrolled in the single and MAD parts of the VH4004280 study, respectively. The study is currently ongoing and remains blinded (3:1 active to placebo random assignment to treatment).

The pharmacokinetic profile of VH4004280 is being initially evaluated following single oral dose administration from **CCI**. Based on the preliminary analysis, VH4004280 has a median **CCI** in concentration and a mean **CCI**. VH4004280 showed a **CCI**. There was an approximately **CCI** from Day 1 in Cmax and AUC0-tau, respectively following **CCI**. Based on the preliminary clinical DDI analysis, VH4004280 **CCI** and thus VH4004280 **CCI**

Overall, there have been no clinically significant safety findings, serious adverse events (SAEs), deaths, pregnancies, trends in vital signs, laboratory parameters, ECG parameters nor discontinuations due to adverse events (AEs). More detailed information can be found in the CIBs [RPS-CLIN-048482; RPS-CLIN-056826].

2.2.3.2. Study 218490 - **CCI FTIH VH4011499**

Study 218490 is an ongoing double-blind (sponsor unblinded), randomized, placebo-controlled, single and multiple-ascending-dose Phase 1 and first time in human study to evaluate the safety, tolerability and pharmacokinetics of VH4011499, when administered

as a **CCI**, in healthy adult participants. The study is also designed to evaluate the DDI potential of VH4011499 and evaluate the safety, tolerability and PK of a VH4011499 **CCI** in comparison with existing data from VH4011499 **CCI**.

Based on preliminary results, 32 participants and 19 participants have been enrolled in the single and MAD parts of the VH4011499 study, respectively. The study is currently ongoing and remains blinded (3:1 active to placebo random assignment to treatment).

The pharmacokinetic profile of VH4011499 is being initially evaluated following single oral dose administration from 25 to 1875 mg **CCI**

CCI. Based on the preliminary analysis, VH4011499 has a median **CCI** and a mean **CCI**.

VH4011499 showed a **CCI** in exposure from **CCI**

CCI. There was an approximately **CCI** in Cmax and AUC0-tau, respectively following **CCI**.

Based on the preliminary clinical DDI analysis, VH4011499 had no effect on the **CCI**

[figure not shown]
CCI and thus VH4011499 **CCI**

Overall, there have been no clinically significant safety findings, deaths, SAEs considered related to treatment, pregnancies, trends in vital signs, laboratory parameters, ECG parameters nor discontinuations due to AEs. More detailed information can be found in the CIB [[RPS-CLIN-056829](#)].

2.2.4. Further Non-clinical Data about VH4004280 and VH4011499

A detailed description of the non-clinical pharmacology, pharmacokinetics, toxicology, virology, and chemistry and manufacturing of VH4004280 and VH4011499 is provided in the respective CIBs [[RPS-CLIN-048482](#); [RPS-CLIN-026329](#); [RPS-CLIN-047476](#); [RPS-CLIN-046304](#); [RPS-CLIN-056829](#); [RPS-CLIN-056826](#)].

CCI

CCI

2.3.1. Risk assessment

Potential Risk of Clinical Significance	Summary of Data/Rationale for Risk	Mitigation Strategy
Study Drug VH4004280 and/or VH4011499		
Drug-induced liver injury (and/or clinically significant liver chemistry elevations for VH4011499 only)	
Nonclinical
 
In vitro, both VH4004280 and VH4011499 inhibited CC1 with IC50 values of CC1 respectively, and the CC1 (b) with IC50 values of CC1 respectively. CC1 can cause CC1 which can cause accumulation of CC1 which may lead to CC1.
 
VH4004280:
 
In the definitive 28-day CC repeat dose dog study with VH4004280, minimally increased mean liver weights and increased total bile acids (1 animal) were seen at CC1, however these were not associated with any microscopic liver findings. At the same dose, there were increases in fibrinogen concentrations in males (1.56X control) and females (1.55X control), and prolongation of activated partial thromboplastin time in females (1.87X control). In the 28-day repeat dose rat study with VH4004280, there were no weight changes and no microscopic findings in the liver. Additionally, there were no bilirubin changes in these studies. Whilst these changes could reflect possible hepatocellular and/or hepatobiliary injury, they were of low magnitude and without correlating histopathological findings.
 
In the definitive 13-week VH4004280 CC1 rat study, treatment related minimal to mild hepatocellular vacuolation was
	
Participants with current or history of liver disease, with coinfection with HBV or HCV or known hepatic or biliary abnormalities are excluded from participation in this study (refer to Section 5.2).
 
Participants will be closely monitored for liver related AE and laboratory abnormalities, including serum total bile acids and coagulation parameters.
 
Liver chemistry participant stopping criteria are defined (refer to Section 7.1.1).

CONFIDENTIAL

218307
Protocol Final

Potential Risk of Clinical Significance	Summary of Data/Rationale for Risk	Mitigation Strategy
	
observed in the highest dose group CCI [REDACTED]. This finding, not considered adverse, consisted of macro and microvesicles in the cytoplasm of centrilobular hepatocytes and correlated to pale discoloration of the liver in two males. Although a statistically significant increase in the mean relative (to body) liver weight occurred in males at this dose, this was largely considered related to body weight decrements. In addition, there were increases in total bilirubin (up to 2.38X control) and total bile acids (up to 2.90X control) at CCI [REDACTED] on Days 28 and 85. There were no treatment-related changes in coagulation parameters in this study. There were no liver-related findings in the definitive 3-month VH4004280 CCI [REDACTED] dog study and no changes in coagulation parameters.
 
VH4011499:
 
In the definitive 13-week VH4011499 CCI [REDACTED] studies in rats and dogs, there were no adverse findings in the liver, including no increases in liver enzymes, total bile acids, bilirubin or coagulation parameters.
 
In the definitive 28-day repeat dose CCI dog study with VH4011499, at the highest dose/NOAEL CCI [REDACTED], there were increases relative to pre-dose in alanine and aspartate aminotransferases (ALT increased by up to 11.3 fold in 4/6 dogs, AST increased by up to 3.0 fold in 2/6 dogs) and glutamate dehydrogenase (GLDH increased by up to 6.2 fold in 4/6 dogs) with no histologic correlates in the liver and no changes in liver weight. No increases in bilirubin were observed. In the definitive 28-day repeat dose study in the rat (highest dose/NOAEL CCI [REDACTED] there were no adverse effects of VH4011499,
	

CONFIDENTIAL

218307
Protocol Final

Potential Risk of Clinical Significance	Summary of Data/Rationale for Risk	Mitigation Strategy
	
including no increases in liver enzymes, total bile acids, bilirubin or coagulation parameters.
 
Clinical (blinded data):
 
No trends in liver or coagulation parameters have been observed in the ongoing Phase 1 oral clinical studies with VH4004280 or VH4011499.
	
Increases in cholesterol and triglycerides	
Nonclinical
 
VH4004280:
 
In the definitive 28-day CCI repeat dose toxicity studies with VH4004280, increases in mean serum total cholesterol concentration were observed in rats and dogs at the highest doses tested (CCI [REDACTED]). Increased triglycerides were also noted in dogs at CCI [REDACTED]. In both species, there were no macroscopic or microscopic changes in the liver at any dose level.
 
In the definitive 3-month VH4004280 CCI [REDACTED] rat study, increases in total cholesterol concentrations (up to 1.70X control) at CCI [REDACTED] on Days 28 and 85 were observed. There were no increases in lipids in the definitive 3-month VH4004280 CCI [REDACTED] dog study.
 
VH4011499:
 
No increases in cholesterol or triglycerides were observed in the definitive 28-day CC or 13-week CCI [REDACTED] toxicity studies in dog and rat with VH4011499.
 
Clinical (blinded data):
	
Participants will be closely monitored for relevant AEs and laboratory abnormalities. Lipid panel is included in routine clinical laboratory tests as detailed in the SoA (Section 1.3).

Potential Risk of Clinical Significance	Summary of Data/Rationale for Risk	Mitigation Strategy
	No trends in lipid parameters have been observed in the ongoing Phase 1 oral clinical studies with VH4004280 or VH4011499.	
Hematology changes	
Nonclinical
 
VH4004280:
 
In the 28-day CCI [REDACTED] dose dog study CCI [REDACTED] CCI [REDACTED] increases in neutrophils and monocyte counts were observed.
 
In the definitive 13-week VH4004280 CCI [REDACTED] rat study, treatment-related hematologic changes were observed at CCI [REDACTED], and included increases in lymphocyte, neutrophil and/or white blood cell counts, decreases in hemoglobin concentration, mean corpuscular hemoglobin, mean corpuscular hemoglobin concentration, increases in red blood cell counts, red cell distribution width concentration and/or in reticulocyte counts. There were no changes in hematology parameters in the definitive 13-week VH4004280 CCI [REDACTED] dog study.
 
VH4011499:
 
No changes in hematology parameters were observed in the definitive 28 day CC or 13-week CC [REDACTED] toxicity studies in dog and rat with VH4011499.
 
Clinical (blinded data):
 
No trends in hematology parameters have been observed in the ongoing Phase 1 oral clinical studies with VH4004280 or VH4011499.
	
Participants will be closely monitored for relevant AEs and laboratory abnormalities. Hematology Panel is included in routine clinical laboratory tests as detailed in the SoA (Section 1.3).
 
See Section 8.3.7 for clinical stopping criteria applicable to this potential risk.

Potential Risk of Clinical Significance	Summary of Data/Rationale for Risk	Mitigation Strategy
Acute pulmonary injury (VH4004280 only)	
Nonclinical
 
In a single dose dose-range finding dog study with VH4004280 [REDACTED], inflammatory changes were noted on lung histology.
 
At [REDACTED] histological findings in the lungs of 3/3 dogs included interstitial expansion containing primarily mononuclear cells and fibrin and multifocal mixed cell bronchioalveolar inflammation with alveolar infiltrates comprising vacuolated macrophages, neutrophils and few, non-vacuolated, mononuclear cells. In some regions, there was damage to the alveolar wall, evidenced by the presence of fibrin (free and phagocytized), hemorrhage and pneumocytes ranging from flattened to larger and vacuolated. These microscopic lung findings correlated to gross changes observed in the lung margins. At [REDACTED] [REDACTED], there were no gross observations at necropsy and histologic changes in the lung consisted of minimal bronchioalveolar mixed cell inflammation in 2/3 dogs. There were no microscopic findings in 3/3 dogs given [REDACTED] [REDACTED]
 
There were no histological findings in the lung in the 28-day definitive rat and dog repeat dose studies ([REDACTED] [REDACTED]) conducted with the VH4004280 [REDACTED] formulation being used in Study 217058. I
 
There were no histological findings in the lung in the VH4004280 definitive [REDACTED] 13-week [REDACTED] in both rat (up to doses of [REDACTED] and dog [REDACTED] [REDACTED]
	
Participants with current or history of respiratory disease are excluded from participation in this study (refer to Section 5.2).
 
Participants will receive VH4004280 by the [REDACTED] [REDACTED] [REDACTED] and lower than those observed in [REDACTED] 28-day toxicity studies in both rat and dog, where there were no histologic findings in the lungs.
 
Participants will be closely monitored for relevant AEs, vital signs and laboratory abnormalities.

CONFIDENTIAL

218307
Protocol Final

Potential Risk of Clinical Significance	Summary of Data/Rationale for Risk	Mitigation Strategy
	No similar findings have been observed in nonclinical studies with VH4011499.	
Effects on embryo-fetal development	
Nonclinical
 
VH4004280:
 
Rats and rabbits were given daily CCI doses of VH4004280 in embryo-fetal development studies. There were no effects on embryo-fetal development parameters or maternal toxicity in rats at up to CCI █. In rabbits, maternal toxicity (body weight losses and reductions in body weight gains) occurred at doses CCI █ in the absence of any effects on food consumption or clinical signs. At CCI █ maternal toxicity resulted in decreased fetal weights and skeletal variations (unossified sternebrae) but no malformations. Similar findings did not occur at lower doses, and these findings are related to maternal toxicity and not direct effects on embryo-fetal development.
 
VH4011499:
 
In embryo-fetal development studies, rats were given daily CC doses and rabbits were given CCI █ of VH4011499. There were no effects on embryo-fetal development parameters or maternal toxicity in rats at up to CCI █. In rabbits, maternal toxicity (reduced body weight gains and food consumption) was noted at CCI █ with no effects on embryo-fetal development parameters at doses up to CCI █
	
Participants of childbearing potential (POCBP) must be using acceptable forms of birth control through to Day 39. POCBP will have pregnancy testing conducted prior to study intervention and during the study.
 
Participants who become pregnant after administration of the first study intervention dose must not receive subsequent doses of the study intervention but may continue other study procedures at the discretion of the investigator.

CONFIDENTIAL

218307
Protocol Final

Potential Risk of Clinical Significance	Summary of Data/Rationale for Risk	Mitigation Strategy
CCI		
CCI [REDACTED] should be dosed with caution if co-administered with VH4004280 from Day 1 through Day 11.
 
CCI [REDACTED] should be dosed with caution if co-administered with VH4011499 or VH4004280 from Day 1 through Day 11. CCI [REDACTED] with CCI [REDACTED] are not permitted from Day 1 through Day 11.

Other (both VH4004280 and VH4011499)		
Emergence of resistance	CCI [REDACTED]	
Short monotherapy period (10 days) followed immediately at the end of the Day 11 visit by initiation of cART.
 
The dose and dose regimens selected are intended to rapidly achieve plasma concentrations that provide therapeutic benefit. The lowest starting dose that is pre-specified aims to target CCI [REDACTED].
 
[REDACTED] is unlikely to occur under these conditions.

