5.1. Inclusion Criteria

Entry into screening nor meeting all eligibility criteria does not guarantee enrollment into the study. To manage the total study enrollment, VH/GSK at its sole discretion, may suspend screening and/or enrollment at any site or study-wide at any time.

Participants are eligible to be included in the study only if all the following criteria apply:

Age

- Participant must be 18 to 65 years of age inclusive at the time of signing the informed consent.

Type of Participant and Disease Characteristics

2. Participants who are overtly healthy (other than HIV-1 infection) as determined by the investigator or medically qualified designee based on a medical evaluation including medical history, physical examination, laboratory tests, and cardiac monitoring.
3. Screening CD4+ T-cell count ≥ 200 cells/ μ L.

- 4. Documented HIV-1 infection and Screening plasma HIV-1 RNA $\geq 3,000$ copies/mL. A single repeat of this test is allowed within a single Screening period to determine eligibility.
- 5. Treatment-naïve: Defined as no ARVs (in combination or monotherapy) received after the diagnosis of HIV-1 infection. Prior use of oral PreP is permitted and meets inclusion. Prior use of parenteral PreP is exclusionary.

Weight

- 6. Body weight ≥ 50.0 kg (110 lbs) for men and ≥ 45.0 kg (99 lbs) for women and body mass index (BMI) within the range 18.5-31.0 kg/m² (inclusive - applies to males and females).

Sex and Contraceptive/Barrier Requirements

- 7. All participants participating in the study should be counseled on safer sexual practices including the use and benefit/risk of effective barrier methods (e.g. male condom) and on the risk of HIV transmission to an uninfected partner.

Participants Male at birth: There are no contraceptive requirements for participants who were male at birth.

Participants Female at birth: A participant who was female at birth is eligible to participate if they are not pregnant and not breastfeeding. Participant of childbearing potential (POCBP) must be using acceptable forms of birth control through to Day 39. The investigator is responsible for review of medical history, menstrual history, and recent sexual activity to decrease the risk for inclusion of a POCBP with an early undetected pregnancy. Refer to Section 10.4 for more details.

Informed Consent

- 8. Capable of giving signed informed consent, which includes compliance with the requirements and restrictions listed in the ICF and stated in this protocol.

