5.2. Exclusion Criteria

Participants are excluded from the study if any of the following criteria apply:

MEDICAL CONDITIONS

1. Women who are breastfeeding or plan to become pregnant or breast feed during the study.
2. Participants with acute HIV infection, evidenced by acute retroviral syndrome (e.g., fever, malaise, fatigue, etc.) and/or evidence of recent (within 3 months) documented viremia without antibody production and/or evidence of recent (within 3 months) documented seroconversion.
3. Any evidence of an active Centers for Disease Control and Prevention (CDC) Stage 3 disease [CDC, 2014], except cutaneous Kaposi's sarcoma not requiring systemic therapy during the study. Refer to Section 10.8 for more details.
4. Untreated syphilis infection [positive rapid plasma reagin (RPR) at screen] without documentation of treatment. Participants who have successfully completed treatment at least 7 days prior to Day 1 are eligible if recruitment is open.
5. Ongoing malignancy other than cutaneous Kaposi's sarcoma, basal cell carcinoma, or resected, non-invasive cutaneous squamous cell carcinoma, or cervical, anal or penile intraepithelial neoplasia; or other localized malignancies require agreement between the investigator and the study VH medical monitor for inclusion of the participant prior to randomization.
6. Treatment with immunomodulating agents (such as systemic corticosteroids, interleukins, interferons) or any agent with known anti-HIV activity (such as hydroxyurea or foscarnet) within 30 days of study drug administration.
7. Any pre-existing physical or mental condition which, in the opinion of the investigator, may interfere with the participant's ability to comply with the dosing schedule and/or protocol evaluations or which may compromise the safety of the participant; Any pre-existing physical or other psychiatric condition (including alcohol or drug abuse), which, in the opinion of the investigator (with or without psychiatric evaluation), could interfere with the participant's ability to comply with the dosing schedule and protocol evaluations or which might compromise the safety of the participant.

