8. Any history of significant underlying psychiatric disorder, in the opinion of the investigator or VH medical monitor, including but not limited to schizophrenia, bipolar disorder with or without psychotic symptoms, other psychotic disorders, or schizotypal (personality) disorder; or a clinical assessment of suicidality based on the responses on the C-SSRS.
9. Any history of major depressive disorder with or without suicidal features, or anxiety disorders, that required medical intervention (pharmacologic or not) such as hospitalization or other inpatient treatment and/or chronic (>6 months) outpatient treatment. Participants with other conditions such as adjustment disorder or dysthymia that have required shorter term medical therapy (<6 months) without inpatient treatment and are currently well-controlled clinically or resolved may be considered for entry after discussion and agreement with the VH medical monitor.

10. Any condition which, in the opinion of the investigator, may interfere with the absorption, distribution, metabolism or excretion of the study drugs or render the participant unable to take oral medication.
11. Current or chronic history of liver disease or known hepatic or biliary abnormalities (except for Gilbert's syndrome or asymptomatic gallstones).
12. A pre-existing condition, in the opinion of the investigator or VH medical monitor, that could interfere with normal gastrointestinal anatomy or motility (e.g., gastroesophageal reflux disease [GERD], gastric ulcers, gastritis, inflammatory bowel disease), hepatic and/or renal function, that could interfere with the absorption, metabolism, and/or excretion of the study interventions or render the participant unable to take oral study treatment.
13. Medical history of cardiac arrhythmias or cardiac disease or a family or personal history of long QT syndrome or sudden cardiac death. Any significant arrhythmia or ECG finding (e.g., prior myocardial infarction, sinoatrial pauses, bundle branch block, or conduction abnormality) which, in the opinion of the investigator or VH medical monitor, will interfere with the safety for the individual participant.
14. Exclusion criteria for screening ECG (a single repeat is allowed for eligibility determination and will be the screening ECG entered into the eCRF):

[figure not shown]
	Males	Females
Heart rate ¹	<45 or >100 bpm	<50 or >100 bpm
PR Interval	<120 or >200 msec	
QRS duration	<70 or >110 msec	

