QTc interval (Fridericia's)	>450 msec	>470 msec

Note: ¹A heart rate from 100 to 110 beats per minute (bpm) can be rechecked by ECG or vitals within 30 minutes to verify eligibility. ²The QTc is the QT interval corrected for heart rate according to Fridericia's formula (QTcF). It is either machine-read or manually over-read. The specific formula used to determine eligibility and discontinuation for an individual participant should be determined prior to initiation of the study. In other words, several different formulas cannot be used to calculate the QTc for an individual participant and then the lowest QTc value used to include or discontinue the participant from the study.

15. To assess any potential impact on participant eligibility regarding safety, the investigator must refer to the CIBs and supplements, approved product labels, and/or local prescribing information for detailed information regarding warnings, precautions, contraindications, AEs, drug interactions, and other significant data pertaining to the study drugs.

PRIOR/CONCOMITANT THERAPY

CCI

17. History of sensitivity to any of the study medications, or their components or drugs of their class, or a history of drug or other allergy that, in the opinion of the investigator or VH medical monitor, contraindicates their participation.
18. Participants who require concomitant medications known to be associated with a prolonged QTc (see list from <https://www.crediblemeds.org>).
19. Treatment with any of the following agents within 28 days of Screening: radiation therapy, cytotoxic chemotherapeutic agents, any systemic immune suppressant.
20. Prior use of **CCI** [REDACTED] for any reason is exclusionary.
21. Participants receiving any protocol-prohibited medication and who are unwilling or unable to switch to an alternate medication.

PRIOR/CONCURRENT CLINICAL STUDY EXPERIENCE

22. The participant has received an investigational HIV vaccine (immunotherapeutic or immunomodulatory).
23. Exposure to an approved vaccine within 14 days prior to Day 1.
24. Exposure to an investigational drug or experimental vaccine within either 28 days, 5 half-lives of the test agent, or twice the duration of the biological effect of the test agent, whichever is longer, prior to the first dose of study intervention.

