8.3.1. Physical examination

- A complete physical examination will include, at a minimum, assessments of the skin, cardiovascular, respiratory, gastrointestinal, and neurological systems.
- A brief physical examination is symptom driven (with the exception of an expected respiratory system assessment at select visits) and may be targeted to include select system/organ assessments. At the discretion of the investigator, a brief physical examination may be made a complete physical examination.
- Investigators should pay special attention to clinical signs related to previous serious illnesses.
- Height and weight measurements will be used to calculate body mass index (BMI).

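### The respiratory-disease exclusion that Protocol Section 2.3.1 relies on for VH4004280 lung risk appears in no visible criterion of Section 5.2

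*Protocol*

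**What the plan says.** The risk table in Protocol Section 2.3.1 lists acute pulmonary injury as a potential risk of VH4004280 only. The first mitigation reads: "Participants with current or history of respiratory disease are excluded from participation in this study (refer to Section 5.2". It is categorical, it covers past as well as current disease, and it names the section where the rule should be found. The other mitigations in that row are exposure lower than in 28-day rat and dog studies that showed no lung histology findings, and monitoring of adverse events, vital signs and laboratory values.

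The liver row of the same table has the same form: "Participants with current or history of liver disease, with coinfection with HBV or HCV or known hepatic or biliary abnormalities are excluded", again with a pointer to Section 5.2.

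Section 5.2 numbers its exclusion criteria 1 to 38. Criterion 11 is the liver rule: "Current or chronic history of liver disease or known hepatic or biliary abnormalities (except for Gilbert's syndrome or asymptomatic gallstones". Criterion 12 covers gastrointestinal, hepatic and renal conditions, and criterion 13 covers cardiac history. There is no counterpart for the lung.

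The text that could reach lung disease is general. Inclusion 2 in Section 5.1 admits "Participants who are overtly healthy (other than HIV-1 infection) as determined by the investigator or medically qualified designee based on a medical evaluation". Exclusion 7 turns on the investigator's opinion that a condition may interfere with compliance with dosing "and/or protocol evaluations or which may compromise the safety of the participant". Exclusion 15 begins: "To assess any potential impact on participant eligibility regarding safety, the investigator must refer to the CIBs and supplements".

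**The concern.** Section 2.3.1 describes a fixed rule and Section 5.2 does not contain it. Ethics committees and regulators weigh the risk from Section 2.3.1, and the benefit-risk conclusion in Section 2.3.3 leans on the measures taken to reduce risk. Sites select participants from Section 5, which forbids waivers and so is meant to be applied as listed. A safeguard presented as automatic is in practice discretionary, and sites may apply it differently.

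Eligibility carries particular weight for this compound. VH4004280 is given once, on Day 1, and the estimand table in Section 3 notes that its discontinuation is not possible. Stopping rules cannot withdraw a dose already taken, so screening is the main protection for the individual before exposure.

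There is a smaller consequence in the SAP. Item 07 of Table 2 (Section 3.1) removes from the Per-Protocol set anyone who breached a listed eligibility criterion. A participant with past respiratory disease would breach none, so item 07 would not apply, although case-by-case adjudication under item 08 could still remove that person.

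**Working it through.** The plan states no figure here, so the main check is a reading of the text.

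**1. Does the pointer resolve?** I read Section 5.2 from criterion 1 to criterion 38.

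- Criteria 1 to 15, under the medical conditions heading, are all visible. None names respiratory, pulmonary or lung disease.
- Criterion 16 is fully redacted. It falls under the prior and concomitant therapy heading, between 15 and 17.
- Criterion 20 is partly redacted, but its visible words concern prior use of an agent.
- The remaining criteria cover therapy, earlier trials, laboratory and diagnostic results, alcohol and drug use. Only no. 31 (COVID-19) touches the lung.

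The liver pointer does resolve: to criterion 11 for liver and biliary disease, and to criteria 28 to 30 for hepatitis B and C. The respiratory pointer resolves to nothing visible.

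**2. Does other text do the same job?**

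- Inclusion 2 and exclusion 7 rest on the judgement of the investigator (or, for inclusion 2, a designee).
- Exclusion 15 tells the investigator to consult documents and states no exclusion of its own.
- Exclusion 3 reaches only active AIDS-defining illness, which Appendix 8 lists as including Pneumocystis pneumonia, recurrent pneumonia and tuberculosis. Exclusion 31 reaches only SARS-CoV-2 infection, suggestive symptoms or recent contact.

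Clinically important lung disease would probably be screened out. Mild or past disease, such as controlled asthma, need not be.

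**3. How many people could this involve?**

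Inputs from the documents: active VH4004280 goes to 6 + 6 = 12 participants in Part 1a, and to 12 + 6 = 18 if Part 2a runs. Randomized participants number 14 + 7 = 21 in those two parts, and up to 42 in the study.

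Assumption: a proportion p of those who pass the discretionary checks still have some current or past respiratory disease. I use p = 2%, 5% and 10%.

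- Expected number dosed = n × p.
- Chance of at least one = 1 − (1 − p)^n. For n = 12 and p = 5%, this is 1 − 0.95^12 = 0.460.
- Extra screen failures if the criterion is added = N/(1 − p) − N. For N = 21 and p = 5%, this is 21/0.95 − 21 = 1.11.

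| p | Expected dosed, n = 12 | At least one, n = 12 | Expected dosed, n = 18 | At least one, n = 18 | Extra failures, N = 21 | Extra failures, N = 42 |
|---|---|---|---|---|---|---|
| 2% | 0.24 | 22% | 0.36 | 31% | 0.43 | 0.86 |
| 5% | 0.60 | 46% | 0.90 | 60% | 1.11 | 2.21 |
| 10% | 1.20 | 72% | 1.80 | 85% | 2.33 | 4.67 |

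These are chances of dosing someone whom Section 2.3.1 says is excluded. They say nothing about the chance of lung injury.

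**4. What is the underlying signal?** The lung findings come from one single-dose, dose-range-finding dog study: changes in 3 of 3 dogs at one dose, minimal inflammation in 2 of 3 at another, and none in 3 of 3 at a third. The definitive studies were clean: "There were no histological findings in the lung in the 28-day definitive rat and dog repeat dose studies", and likewise in the 13-week studies.

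**The case against.** The strongest reply has four parts.

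First, criterion 16 cannot be read, and headings in Section 5.2 are an imperfect guide to content: criterion 17, under the same therapy heading, is about sensitivity and allergy. That caveat stands. Even so, every criterion under medical conditions is visible, and the sponsor published the respiratory sentence in Section 2.3.1 unredacted, so there is no evident reason to hide its counterpart.

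Second, the general criteria are not empty. The complete examination at screening must include the respiratory system, and a medical history is taken. Section 2.3.1 is itself protocol text that sites receive, so it is an inference that they would act on Section 5 alone. This lowers the likelihood of a problem but does not turn a discretionary test into the categorical rule that Section 2.3.1 describes.

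Third, the safety context is reassuring. Section 2.2.3.1 reports 41 single-dose and 18 multiple-dose participants in the ongoing first-in-human study (blinded, 3:1 active to placebo) with no clinically significant safety findings. The pausing rules in Section 8.3.7 would act on attributable, clinically significant SAEs and attributable Grade 4 events. Section 8.3.1 also provides for lung examination: it describes the brief examination as symptom driven, "with the exception of an expected respiratory system assessment at select visits". All of this limits the consequence. None of it supplies the exclusion.

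Fourth, the prevalence range is assumed, so the probabilities contain no trial data. That is right. They only size the gap, and the inconsistency does not depend on them.

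**Conclusion.** The concern holds. Section 2.3.1 claims a categorical exclusion that the visible text of Section 5.2 does not contain, and the substitutes are discretionary or narrow. The only textual uncertainty is redacted criterion 16.

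The statistical consequence is slight. The primary analysis uses the Full Analysis Set and is unaffected; Table 2 of the SAP governs only the Per-Protocol set, used for sensitivity and supplementary analyses. No added risk of lung injury has been shown. What matters is that a safety measure presented to reviewers is not put into effect at enrolment, for a single-dose drug that cannot be withdrawn once given. It should be fixed, but it does not undermine the trial.

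**What to change.** Bring the two sections into agreement.

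- **Preferred:** add a numbered respiratory-disease exclusion to Section 5.2, at least for Parts 1a and 2a. The sponsor's clinical team should set its scope: current disease, past disease or both, and which diagnoses. A breach would then fall under item 07 of SAP Table 2 without any change to the SAP.
- **Weaker alternative, if no categorical exclusion is intended:** correct Section 2.3.1 to say that respiratory history is assessed by the investigator under inclusion 2 and exclusions 7 and 15, and restate the mitigation as exposure limits plus monitoring.

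If criterion 16 is in fact the respiratory rule, the sponsor need only confirm that.

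Either change is one criterion or one sentence in an amendment. On the assumed range, adding the criterion costs the few extra screen failures tabulated above, with the lower figures applying if it is confined to the VH4004280 parts. Rewording Section 2.3.1 costs none.
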